7.2. Demographic/Medical History and Baseline Assessments

The following demographic parameters will be captured during Screening: date of birth, gender, race and ethnicity.

Medical/medication history assessed as related to the eligibility criteria listed in Section 5.2.

Baseline (Screening) assessments obtained will include:

- Complete physical examination, including height (in cm) and weight (in kg).
- Vital signs: blood pressure, temperature, respiratory rate, pulse rate
- Eastern Cooperative Oncology Group (ECOG) performance status
- Clinical laboratory tests: hematology, clinical chemistry and urinalysis
- Serum beta-human chorionic gonadotropin (β -HCG) pregnancy test for female subjects of childbearing potential only
- 12-lead electrocardiogram (ECG)
- Echocardiogram (ECHO) or multi-gated acquisition (MUGA) scan
- Brain magnetic resonance imaging (MRI) with contrast or a computed tomography (CT) scan (with/without contrast) if MRI is contraindicated for all subjects with cutaneous melanoma
- Ophthalmic exam by an ophthalmologist
- Review of concomitant medications

Procedures conducted as part of the subject's routine clinical management (e.g., blood count, imaging study) and obtained prior to signing of informed consent may be utilized for Screening or baseline purposes provided the procedure meets the protocol-defined criteria and has been performed in the timeframe of the study.

7.2.1. Critical Baseline Assessments

Critical baseline assessments include height, weight, blood pressure, smoking history, medical conditions and family history of cardiovascular disease and risk factors, and stage of disease at screening.

CONFIDENTIAL

7.3. Safety Evaluations

Planned time points for all safety assessments are provided in the Time and Events Table (Section 7.1).

7.3.1. Physical Examinations

A complete physical examination will include assessments of the head, eyes, ears, nose, throat, skin, thyroid, neurological, lungs, cardiovascular, abdomen (liver and spleen), lymph nodes and extremities. Height and weight will also be measured and recorded.

A brief physical examination will include assessments of the skin, lungs, cardiovascular system, and abdomen (liver and spleen).

7.3.2. ECOG Performance Status

The performance status will be assessed using the Eastern Cooperative Oncology Group (ECOG) scale (Appendix 4) as specified in the Time and Events Table (see Section 7.1).

7.3.3. Vital Signs

Vital sign measurements will include (i.e., systolic and diastolic blood pressure, temperature, respiration rate and pulse rate). Vital signs should be measured after resting for at least 5 minutes in a semi-supine position. Vital signs will be measured more frequently if warranted by clinical condition of the subject. On days where vital signs are measured multiple times, temperature does not need to be repeated unless clinically indicated.

7.3.4. Electrocardiogram (ECG)

A single 12-lead ECG will be obtained at designated time points during the study using an ECG machine that automatically calculates the heart rate and measures PR, QRS, QT, and corrected QT (QTc) intervals. At each assessment a 12-lead ECG will be performed by qualified personnel at the site after the subject has at least a 5 minute rest and is in a semi-recumbent or supine position.

The QT interval should be corrected for heart rate by Bazette's formula (QTcB; see Appendix 6). Refer to Section 3.10.2 for QTc stopping criteria and additional information.

7.3.5. Echocardiogram (ECHO) and/or Multi-gated Acquisition (MUGA) Scans

An ECHO (preferred) or a MUGA scan will be performed at baseline to assess cardiac ejection fraction and cardiac valve morphology for the purpose of study eligibility, as specified in the Time and Events Table (see Section 7.1). Additional ECHO or MUGA assessments may be performed if clinically warranted. The procedure used to document the subject's baseline LVEF status should be used consistently throughout the study. If possible, the interpretation of LVEF status should be performed consistently by the same reviewer throughout the study. The evaluation of the echocardiographer should include

CONFIDENTIAL

an evaluation for left ventricular ejection fraction (LVEF) and both right and left-sided valvular lesions.

Copies of all ECHO or MUGA scans performed on subjects who experience an absolute decrease >10% in LVEF compared to baseline concurrent with LVEF < institutional lower limit of normal (LLN) may be required by the Coordinating Center for review.

7.3.6. Brain MRI and/or CT Scan

A magnetic resonance imaging (MRI) with contrast will be performed at Screening (see Time and Events Table, Section 7.1) to rule out any new untreated brain metastases and to verify stability of brain metastases if present for all subjects with cutaneous melanoma. A computed tomography (CT) scan with and without contrast may be performed if a MRI is contraindicated.

7.3.7. Laboratory Assessments

All protocol required laboratory assessments should be performed according to the Time and Events Table (see Section 7.1).

Prior to administration of the first dose of study treatment, results of laboratory assessments should be reviewed. Any laboratory test with a value outside the normal range may be repeated (prior to the first dose) at the discretion of the investigator.

If laboratory assessments for screening are completed within 72 hours of the first dose, they do not have to be repeated on cycle 1, day 1. If labs are obtained on the first day, values are still required to meet inclusion criteria (Table 13).

If additional non-protocol specified laboratory assessments are performed at the institution's local laboratory and result in a change in patient management or are considered clinical significant by the Investigator (for example SAE or AE or dose modification) the results must be recorded in the subject's CRF.

All laboratory tests with abnormal values that are considered clinically significant during participation in the study or within 30 days after the last dose of study treatment should be repeated until the values return to normal or baseline. If such values do not return to normal within a period judged reasonable by the investigator, the possible etiology should be identified and the Coordinating Center notified.

Hematology, clinical chemistry, urinalysis and additional parameters to be tested are listed in Table 15:

CONFIDENTIAL

Table 15 List of Clinical Laboratory Tests

Hematology			
Platelet Count		RBC Indices:	Automated WBC Differential:
Red blood cell (RBC) Count		MCV	Neutrophils
White blood cell (WBC) Count (absolute)		MCH	Lymphocytes
		MCHC	Monocytes
Hemoglobin			Eosinophils
Hematocrit			Basophils
International Normalized Ratio (INR; at screening only) ^a			
Prothrombin time (PT; at screening only) ^a			
Partial thromboplastin time (PTT; at screening only) ^a			
Clinical Chemistry			
Blood urea nitrogen (BUN)	Potassium	Aspartate aminotransferase (AST)	Total and direct bilirubin
Creatinine ^b	Chloride	Alanine aminotransferase (ALT)	
Glucose, (random)	Total carbon dioxide (CO ₂)		Albumin
Sodium	Calcium	Alkaline phosphatase	
Lactate		Potassium	
Dehydrogenase (LDH)			
Routine Urinalysis			
Specific gravity			
pH, glucose, protein, blood and ketones by dipstick			
Microscopic examination (if blood or protein is abnormal)			
Other screening tests			
Human Immunodeficiency virus (HIV) ^c			
Hepatitis B (HBsAg)			
Hepatitis C (Hep C antibody -- if second generation Hepatitis C antibody positive, a hepatitis C antibody Chiron RIBA [®] immunoblot assay should be reflexively performed on the same sample to confirm the result)			
Follicle stimulating hormone (FSH) and estradiol (as needed in women of non-child bearing potential only)			
a. Coagulation panel to be done at Screening only			
b. If serum creatinine is > 1.5 mg/dL, creatinine clearance should be calculated using the standard Cockcroft-Gault formula (Appendix)			
c. HIV testing is optional			

7.3.8. Ophthalmic Examination

Subjects are required to have a standard ophthalmic examination performed by an ophthalmologist at the times described (Section 7.1). At certain time points in the trial and if visual changes develop, an eye exam is indicated. (Refer to Table 6 for visual changes stopping criteria). The exam will include best corrected visual acuity, tonometry, slit lamp biomicroscopic examination, visual field examination, and dilated indirect funduscopy with special attention to retinal abnormalities. Optical coherence tomography is strongly recommended at scheduled visits, and if retinal abnormalities are suspected. Other types of ancillary testing including color fundus photography and

CONFIDENTIAL

fluorescein angiography are also recommended if clinically indicated.

CONFIDENTIAL

7.3.9. Pregnancy Testing and Reporting

The need for a screening pregnancy test depends on whether a female subject is of childbearing potential or non-childbearing potential.

If a female subject is of childbearing potential, she must have a serum β -HCG pregnancy test performed within 14 days prior to the first dose of study treatment(s). Subjects with positive pregnancy test result must be excluded from the study. Subjects with negative pregnancy test result must agree to use an effective contraception method as described (Section 11.1.1) during the study until four months following the last dose of study treatment(s).

Any pregnancy that occurs during study participation must be reported using a clinical trial pregnancy form. To ensure subject safety, each pregnancy must be reported to the Coordinating Center within two weeks of learning of its occurrence. The pregnancy must be followed up to determine outcome (including premature termination) and status of mother and child. Pregnancy complications and elective terminations for medical reasons must be reported as an adverse event (AE) or serious adverse event (SAE). Spontaneous abortions must be reported as an SAE.

Any SAE occurring in association with a pregnancy brought to the investigator's attention after the subject has completed the study and considered by the investigator as possibly related to the study treatment(s), must be promptly reported to the Coordinating Center.

In addition, the investigator must attempt to collect pregnancy information on any female partners of male study subjects who become pregnant while the subject is enrolled in the study. Pregnancy information must be reported to the Coordinating Center as described above.

7.4. Baseline Assessment of Target and non-target lesions

All baseline lesion assessments must be performed within 28 days of enrollment.

- Lymph nodes that have a short axis of <10mm are considered non-pathological and should not be recorded or followed.
- Pathological lymph nodes with <15mm and but \geq 10mm short axis are considered non measurable.
- Pathological lymph nodes with \geq 15mm short axis are considered measurable and can be selected as target lesions; however lymph nodes should not be selected as target lesions when other suitable target lesions are available.
- Measurable lesions up to a maximum of two lesions per organ and five lesions in total, representative of all involved organs, should be identified as target lesions, and recorded and measured at baseline. These lesions should be selected on the basis of their size (lesions with the longest diameter) and their suitability for accurate repeated measurements (either by imaging techniques or clinically).

Note: Cystic lesions thought to represent cystic metastases should not be selected as target lesions when other suitable target lesions are available.

CONFIDENTIAL

Note: Measurable lesions that have been previously irradiated and have not been shown to be progressing following irradiation should not be considered as target lesions.

- Lytic bone lesions or mixed lytic-blastic lesions, with identifiable soft tissue components, that can be evaluated by CT or MRI can be considered measurable. Bone scans, FDG-PET scans or X-rays are not considered adequate imaging techniques to measure bone lesions.
- All other lesions (or sites of disease) should be identified as non-target and should also be recorded at baseline. Non-target lesions will be group by organ. Measurements of these lesions are not required, but the presence or absence of each should be noted throughout follow-up.

7.5. Efficacy Assessments

Disease progression and response evaluations will be determined according to the definitions established in the Response Evaluation Criteria in Solid Tumors (RECIST version 1.1) [Eisenhauer, 2009].

See the Time and Events Table (Section 7.1) for the schedule of efficacy assessments. Assessments must be performed on a calendar schedule and should not be affected by dose interruptions/delays.

The following are required at baseline:

- Computed tomography (CT) scan with contrast (e.g., chest, abdomen, and/or pelvis as appropriate for a given subject) for assessment of baseline disease burden within four weeks of enrollment. All post- treatment assessments require CT imaging of disease sites identified by these baseline scans.
NOTE: Although CT is preferred, MRI may be used as an alternative method of baseline disease assessment, especially for those subjects where CT is contraindicated (i.e., allergy), provided that the method used to document baseline status is used consistently throughout study treatment to facilitate direct comparison.
- A baseline brain scan is required for all subjects for assessment of CNS disease within four weeks of enrollment. Head CT with contrast or magnetic resonance imaging (MRI) are both acceptable methods of CNS disease assessment, but contrast enhanced MRI is preferred. For subjects without CNS disease at baseline, subsequent brain scans should only be performed as clinically indicated (i.e., symptoms suggestive of CNS progression). Subjects demonstrating brain metastasis at baseline must have the baseline scan compared to an earlier scan performed (preferably 6 weeks earlier) to demonstrate that the metastasis is stable. Stable is defined as no increase in lesions between the two scans. The radiologist reports and the primary investigator's analysis for these scans must be sent to the medical monitor for approval. Timing between the baseline scan and original scan is described above.

CONFIDENTIAL

NOTE: For subjects with CNS disease at baseline, a brain scan is required every eight weeks or as clinically indicated.

NOTE: The method used to document baseline status should be used consistently throughout study treatment to facilitate direct comparison

For subjects with palpable/superficial lesions, clinical disease assessments by physical examination should be performed at baseline and throughout study treatment as clinically indicated.

Confirmation of CR and PR are required per protocol. Confirmation assessments must be performed no less than four weeks after the criteria for response have initially been met and may be performed at the next protocol scheduled assessment. If a confirmation assessment is performed prior to the next protocol schedule assessment, the next protocol scheduled evaluation is still required (e.g., evaluations must occur at each protocol scheduled time point regardless of unscheduled assessments).

7.5.1 Assessment Guidelines

Please note the following:

- The same diagnostic method, including use of contrast when applicable, must be used throughout the study to evaluate a lesion.
- All measurements should be taken and recorded in millimeters (mm), using a ruler or calipers.
- Ultrasound is not a suitable modality of disease assessment. If new lesions are identified by ultrasound, confirmation by CT or MRI is required.
- FDG-PET is generally not suitable for ongoing assessments of disease. However FDG-PET can be useful in confirming new sites of disease where a positive FDG-PET scan correlates with the new site of disease present on CT/MRI or when a baseline FDG-PET was previously negative for the site of the new lesion.
- If PET/CT is performed then the CT component can only be used for standard response assessments if performed to diagnostic quality, which includes the required anatomical coverage and prescribed use of contrast. The method of assessment should be noted as CT on the electronic CRF.

Clinical Examination: Clinically detected lesions will only be considered measurable when they are superficial (e.g., skin nodules). In the case of skin

CONFIDENTIAL

lesions, documentation by color photography, including a ruler or calipers to measure the size of the lesion, is required.

CT and MRI: Contrast enhanced CT with 5mm contiguous slices is recommended.

Minimum size of a measurable baseline lesion should be twice the slice thickness, with a minimum lesion size of 10 mm when the slice thickness is 5 mm. MRI is acceptable, but when used, the technical specification of the scanning sequences should be optimized for the evaluation of the type and site of disease and lesions must be measured in the same anatomic plane by use of the same imaging examinations. Whenever possible, the same scanner should be used (Eisenhauer 2009).

X-ray: Should not be used for target lesion measurements owing to poor lesion definition.

Lesions on chest X-ray may be considered measurable if they are clearly defined and surrounded by aerated lung; however chest CT is preferred over chest X-ray.

Brain Scan: If brain scans are required, then contrast enhanced MRI is preferable to contrast enhanced CT.

7.5.2 Measurable and Non-measurable Definitions

A measurable lesion is a non-nodal lesion that can be accurately measured in at least one dimension (longest dimension) of:

- ≥ 10 mm with MRI or CT when the scan slice thickness is no greater than 5mm. If the slice thickness is greater than 5mm, the minimum size of a measurable lesion must be at least double the slice thickness (e.g., if the slice thickness is 10 mm, a measurable lesion must be ≥ 20 mm).
- ≥ 10 mm caliper/ruler measurement by clinical exam or medical photography.
- ≥ 20 mm by chest x-ray.

Additionally lymph nodes can be considered pathologically enlarged and measurable if:

- ≥ 15 mm in the short axis when assessed by CT or MRI (slice thickness recommended to be no more than 5 mm). At baseline and follow-up, only the short axis will be measured (Eisenhauer 2009).

A non-measurable lesion is:

- All other lesions including lesions too small to be considered measurable (longest diameter < 10 mm or pathological lymph nodes with ≥ 10 mm and < 15 mm short axis) as well as truly non-measurable lesions, which include: ascites, pleural or pericardial effusions, inflammatory breast disease, lymphangitic involvement of the skin or lung, abdominal

CONFIDENTIAL

masses/abdominal organomegaly identified by physical exam that is not measurable by reproducible imaging techniques (Eisenhauer 2009).

Measurable disease: The presence of at least one measurable lesion. Palpable lesions that are not measurable by radiologic or photographic evaluations may not be utilized as the only measurable lesion.

Non-Measurable only disease: The presence of only non-measurable lesions. Note: non-measurable only disease is not allowed per protocol.

7.5.3 Response Criteria

7.5.3.1 Target Lesions

Definitions for assessment of response for target lesion(s) are as follows:

- **Complete Response (CR):** Disappearance of all target lesions. Any pathological lymph nodes must be <10 mm in the short axis.
- **Partial Response (PR):** At least a 30% decrease in the sum of the diameters of target lesions, taking as a reference, the baseline sum of the diameters (e.g. percent change from baseline).
- **Stable Disease (SD):** Neither sufficient shrinkage to qualify for PR nor sufficient increase to qualify for progressive disease.
- **Progressive Disease (PD):** At least a 20% increase in the sum of the diameters of target lesions, taking as a reference, the smallest sum of diameters recorded since the treatment started (e.g. percent change from nadir, where nadir is defined as the smallest sum of diameters recorded since treatment start). In addition, the sum must have an absolute increase from nadir of 5mm.
- **Not Applicable (NA):** No target lesions at baseline.
- **Not Evaluable (NE):** Cannot be classified by one of the five preceding definitions.

NOTE:

- If lymph nodes are documented as target lesions the short axis is added into the sum of the diameters (e.g. sum of diameters is the sum of the longest diameters for non-nodal lesions and the short axis for nodal lesions). When lymph nodes decrease to non-pathological size (short axis <10mm) they should still have a measurement reported in order not to overstate progression.
- If at a given assessment time point all target lesions identified at baseline are not assessed, sum of the diameters cannot be calculated for purposes of assessing CR, PR, or SD, or for use as the nadir for future assessments. However, the sum of the diameters of the assessed lesions and the percent change from nadir should be calculated to ensure that progression has not been documented. If an assessment of PD cannot be made, the response assessment should be NE.

CONFIDENTIAL

- All lesions (nodal and non-nodal) should have their measurements recorded even when very small (e.g., 2 mm). If lesions are present but too small to measure, 5 mm should be recorded and should contribute to the sum of the diameters, unless it is likely that the lesion has disappeared in which case 0 mm should be reported.
- If a lesion disappears and reappears at a subsequent time point it should continue to be measured. The response at the time when the lesion reappears will depend upon the status of the other lesions. For example, if the disease had reached a CR status then PD would be documented at the time of reappearance. However, if the response status was PR or SD, the diameter of the reappearing lesion should be added to the remaining diameters and response determined based on percent change from baseline and percent change from nadir.

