2. OBJECTIVES AND ENDPOINTS

Table 1 lists the objectives and corresponding endpoints.

Table 1 Objectives and Endpoints

	Objectives	Endpoints
Primary	1. To determine the clinical efficacy of trametinib in advanced BRAF nonV600 ^{MUT} melanoma (“high activity” group)	1. Overall response rate (primary statistical endpoint), duration of response, clinical benefit (CR+PR+SD) per RECIST v. 1.1.
Secondary	1. To characterize the safety of trametinib 2. To evaluate the	1. Safety and tolerability as measured by clinical assessments including vital signs and physical examinations, 12-lead

CONFIDENTIAL

[figure not shown]
	time to progression (TTP) and overall survival (OS) of trametinib in advanced BRAF nonV600 ^{MUT} melanoma	electrocardiograms (ECG), echocardiogram (ECHO) or Multi Gated Acquisition (MUGA) scans, chemistry and hematology laboratory values, and adverse events (AEs). 2. TTP and overall survival.
Exploratory	1. To determine the clinical efficacy of trametinib in advanced BRAF nonV600 ^{MUT} melanoma (“low activity/unknown” group) 2. Identify mechanisms of resistance to trametinib in this patient population	1. Overall response rate, duration of response, clinical benefit (CR+PR+SD) per RECIST v. 1.1. 2. Assess molecular characteristics of patient samples, including archival samples, pre-treatment, early while on treatment, and/or at the time of progression

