7.5.3.5 Evaluation of best overall response

The best overall response is the best response recorded from the start of the treatment until disease progression/recurrence and will be determined programmatically by the study investigator.

- To be assigned a status of SD, the post-baseline disease assessment must have met the SD criteria at least once after study Day 1.

CONFIDENTIAL

- If the minimum time for SD is not met, best response will depend on the subsequent assessments. For example if an assessment of PD follows the assessment of SD and SD does not meet the minimum time requirement the best response will be PD. Alternative subjects lost to follow-up after an SD assessment not meeting the minimum time criteria will be considered not evaluable.

Confirmation Criteria:

To be assigned a status of PR or CR, a confirmatory disease assessment should be performed no less than 28 days after the criteria for response are first met. Electronic scans will be required for independent review.

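### The nadir in section 7.5.3.1 omits the baseline sum, so as written target-lesion growth alone at a first on-treatment scan is not PD, in conflict with the plan's own reliance on RECIST 1.1

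*Combined protocol and SAP*

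**What the plan says.** Section 7.5.3.1 sets out the target-lesion rules.

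- **PD** requires "At least a 20% increase in the sum of the diameters of target lesions". What that increase is measured from is stated first in these words: "taking as a reference, the smallest sum of diameters recorded since the treatment started". The bullet then repeats the reference in brackets: "where nadir is defined as the smallest sum of diameters recorded since treatment start". It adds that "the sum must have an absolute increase from nadir of 5mm".
- **PR** uses a different reference, "taking as a reference, the baseline sum of the diameters".
- **SD** is whatever is neither PR nor PD. **NE** is whatever fits none of the other categories.

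Table 14 (section 7.1) and its footnote 14 place the baseline scan at screening, within 28 days of the first dose. The first scheduled scan after that is at week 8.

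Section 7.5 says that progression and response follow the RECIST 1.1 definitions. Section 13.3.2.2.2 says the same of the progression component of PFS.

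Table 1 lists "clinical benefit (CR+PR+SD) per RECIST v. 1.1" among the endpoints of the primary objective, with overall response rate marked as the primary statistical endpoint. TTP (Table 1) and PFS (sections 3.5.4 and 13.3.2.2.2) are secondary.

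For best overall response, section 7.5.3.5 says that for SD the assessment "must have met the SD criteria at least once after study Day 1". It continues: "If the minimum time for SD is not met, best response will depend on the subsequent assessments". No minimum time is stated.

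**The concern.** The progression rule gives its reference sum twice, and both times limits it to sums taken after treatment began. Baseline is named where it is meant, for PR, and a later note on reappearing lesions lists change from baseline and change from nadir as separate quantities. A literal reader therefore has grounds to leave baseline out of the nadir.

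At the first on-treatment scan that leaves no usable reference. A patient whose target lesions have grown well beyond 20% from baseline, with no new lesion and no non-target progression, would not be PD.

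Two sets of results are exposed. Clinical benefit would count some growing tumours as SD. TTP and PFS would record progression at a later scan. Both errors favour trametinib. The study has no concurrent control, so no comparator carries the same error.

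**Working it through.** **1. The plan's own figures, and whether they are touched.** Table 20 follows from the two-stage rule: stop if 0 of 15 respond, reject the null if at least 4 of 25 respond.

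- Early stopping = (1 − p)^15. At p = 0.05 this is 0.4633 (plan: 0.463). At p = 0.25 it is 0.0134 (plan: 0.013).
- Rejection = Σ over x = 1 to 15 of P(X₁ = x) × P(X₂ ≥ max(0, 4 − x)), with X₁ ~ Bin(15, p) and X₂ ~ Bin(10, p). At p = 0.05 this is 0.0336 (plan: 0.034). At p = 0.25 it is 0.9008 (plan: 0.901).

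The other four rows also agree to rounding. CR and PR do not use the nadir, so none of these figures depends on its definition.

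**2. Applying the PD rule to example sums (mm).** PD requires sum ≥ 1.2 × nadir and sum − nadir ≥ 5.

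| Baseline | Week 8 | Week 16 | As written | Baseline counted in nadir |
|---|---|---|---|---|
| 50 | 60 | – | SD | PD (+20%, +10 mm) |
| 50 | 80 | – | SD | PD (+60%, +30 mm) |
| 50 | 80 | 90 | SD, SD | PD at week 8 |
| 50 | 80 | 96 | SD, PD | PD at week 8 |
| 50 | 40 | 50 | SD, PD | SD, PD |

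In the as-written column, the week-8 sum is the only sum since treatment began, so change from nadir is 0%. In row 3 the week-16 change is 90/80 − 1 = 12.5%, still short of 20%, so the delay can exceed one scan interval. In row 4 it is 96/80 − 1 = 20%. Row 5 shows that the two readings agree once the tumour has first shrunk.

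**3. SD or NE.** A note in 7.5.3.1 treats the nadir as a value carried forward to later assessments. If it must be an earlier sum, and baseline is not eligible, the week-8 change is undefined and the target response would be NE. Table 16 then gives overall NE when there is no new lesion and no non-target PD. NE does not count towards clinical benefit at that scan, but progression is still missed there. In row 3 the patient would reach SD at week 16.

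**4. Link to the minimum SD time.** With only the stated condition, a single SD at week 8 is enough for a best response of SD. Under 7.5.3.5, an SD that falls short of the minimum time and is followed by PD becomes a best response of PD. Whether row 4 ends as SD or PD therefore turns on a value that is not given.

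**5. Size, as an illustration.** Inputs are the median PFS on trametinib in section 1.2.4: 2.0 months in V600 wild-type melanoma and 4.8 months in V600-mutant melanoma. Week 8 is 56/30.4375 = 1.84 months. With exponential PFS, the share with an event by week 8 is 1 − 2^(−1.84/median):

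- median 2.0: 1 − 2^(−0.92) = 47%
- median 4.8: 1 − 2^(−0.383) = 23%

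Assume that 30% to 70% of these events rest on target-lesion growth alone. The documents give no figure for this share. In 25 patients:

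- median 2.0: 25 × 0.471 × 0.30 = 3.5, to 25 × 0.471 × 0.70 = 8.2
- median 4.8: 25 × 0.233 × 0.30 = 1.7, to 25 × 0.233 × 0.70 = 4.1

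Overall this is about 2 to 8 of 25.

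**The case against.** The strongest answer is that the plan defers to RECIST 1.1 throughout: in Table 1 for clinical benefit, in 3.5.4 for response, in 7.5 for progression and response, and in 13.3.2.2.2 for PFS. Nothing presents 7.5.3.1 as a departure from that standard, and nothing says that growth over baseline at week 8 is to be recorded as SD. Investigators and independent reviewers may well apply the standard in full. Derivation details are also left to a Reporting and Analysis Plan that is not among the documents and may settle the point.

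This stands as far as it goes. It makes the problem a conflict between a local definition and the cited standard, and not an operative bar on PD at week 8. It does not remove the conflict. Section 7.5.3 writes out its own definitions, no sentence gives precedence, and 7.5.3.5 has the study investigator determine best response programmatically, which is where a written definition is likely to be followed to the letter.

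Three further limits also stand:

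- PD by new lesions or by unequivocal non-target progression can be called at any scan, including week 8 (7.5.3.2 to 7.5.3.4).
- An unscheduled on-treatment scan before week 8 would supply an earlier sum.
- The 2.0-month median may be pessimistic for Cohort A. It comes from a mixed wild-type group in which patients also wild type for NRAS responded more often (20% against 0%). This trial excludes NRAS codon 12, 13 and 61 mutations, and Cohort A was chosen for predicted MEK-inhibitor sensitivity.

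**Conclusion.** The point holds as a defect in a definition. Section 7.5.3.1, applied as written, has no earlier reference sum at a first on-treatment scan. Target-lesion growth over baseline alone would therefore be SD or NE, in conflict with the sections that assign progression to RECIST 1.1. Clinical benefit, TTP and PFS are exposed, in the drug's favour. The primary response-rate test and Table 20 are not.

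The estimate of about 2 to 8 of 25 patients is conditional on three things: literal use of the wording, exponential PFS with one of the two cited medians, and the assumed 30% to 70% share.

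A reader might infer more than the documents support:

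- **That PD cannot be called at week 8, or that growth is in fact counted as SD.** The RECIST 1.1 references and the other routes to PD rule out so flat a statement, and even the strict reading does not settle between SD and NE.
- **That a large bias in clinical benefit is established.** A figure built on the 2.0-month median alone ignores the lower case that the 4.8-month median gives, and the share due to target growth has no source in the plan.
- **That patients with growing tumours would necessarily stay on treatment.** Section 6.3 also allows discontinuation at the investigator's discretion.

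The unstated minimum SD time is a secondary gap. Alone it would be missing detail. It matters here because it helps decide how an SD call at week 8 counts in best response.

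**What to change.** - **7.5.3.1:** define the nadir as the lowest sum of diameters measured on study, with the baseline sum included, and use the same reference in both places in the PD bullet.
- **7.5:** reconcile this with the RECIST 1.1 reference, and say which text governs if the local definitions and the standard differ. Carry the same definition into the Reporting and Analysis Plan.
- **7.5.3.5, as a secondary clarification:** give the minimum SD time a value, tied to the first scheduled scan and its window of plus or minus 7 days.

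The cost is one or two sentences, with no new data and no change to the sample size or the primary test. Clinical benefit and PFS may look slightly less favourable than under the literal wording.
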